6.5.2 Adverse Events of Special Interest

Selected non-serious and SAEs are of special interest and will require immediate reporting, recording, and follow-up. The following events will be closely monitored:

- Treatment-emergent suicidal ideations with intent, with or without a plan, (ie, Type 4 or 5 on the C-SSRS) or any suicidal behaviors
- Treatment-emergent elevated ALT or AST lab value that is $\geq 3 \times \text{ULN}$
- Potential Hy's law cases: elevated ALT or AST lab value that is $\geq 3 \times \text{ULN}$ and an elevated total bilirubin lab value that is $\geq 2 \times \text{ULN}$ and, at the same time, an alkaline phosphatase lab value that is $< 2 \times \text{ULN}$.

Reporting requirements for ALT or AST elevations and potential Hy's law cases are outlined in Sections 9.5 and 9.5.1. Responses to the C-SSRS that meet the above criterion will be captured on the eTablet and monitored by the sponsor. These AEs or events that are determined to be SAEs must be reported appropriately via the designated eCRF and safety forms.

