9.5 ALT or AST Elevations

A treatment-emergent ALT $\geq 3 \times$ ULN and/or AST $\geq 3 \times$ ULN is considered an AE of special interest. Any participant with this laboratory result after study intervention was taken must have repeat testing within 48 to 72 hours to confirm the abnormality. For this repeat testing, the following laboratory tests must be drawn: hematology and chemistry panels, INR, serum acetaminophen level, urine drugs of abuse screen, and blood alcohol level. An extra blood serology sample must be collected and sent to the central laboratory for further diagnostic testing, at a later date, if needed. In addition, the investigator will perform a complete history and examination to evaluate the participant for possible liver disease.

All AEs of special interest must be reported to the sponsor within 24 hours of the time the investigator becomes aware of the event using the abnormal liver function reporting form and the AE eCRF. All new elements of history, physical examination, diagnostic testing results, and other relevant medical reports are to be reported for each AE of special interest.

If an ALT or AST $\geq 3 \times$ ULN is confirmed, close medical follow-up is required:

For these participants, the following laboratory tests must be performed: anti-hepatitis A IgM, hepatitis B surface antigen, anti-hepatitis B core IgM, hepatitis C antibody, hepatitis C quantitative RNA by polymerase chain reaction, anti-hepatitis E IgM, anti-hepatitis E IgG, Cytomegalovirus IgM antibody, and Epstein-Barr Virus IgM antibody. The participant must be followed clinically and further medical evaluation (for other causes of acute hepatic injury) should be done per the judgment of the investigator and in conjunction with medical personnel at the sponsor. In general, the chemistry panel should be repeated 1 to 2 times per week to follow the course of ALT/AST elevation.

Study intervention must be discontinued if any of the following criteria are met:

- ALT or AST $\geq 3 \times$ ULN and the participant is symptomatic with the appearance of fatigue, nausea, vomiting, right upper quadrant pain or tenderness, fever, rash, or eosinophilia ($> 5\%$)
- ALT or AST $\geq 3 \times$ ULN and total bilirubin $> 2 \times$ ULN
- ALT or AST $\geq 3 \times$ ULN and INR > 1.5
- ALT or AST $\geq 5 \times$ ULN for more than 2 weeks
- ALT or AST $\geq 8 \times$ ULN

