The participant may be rechallenged with study intervention only after consultation with the sponsor medical monitor. For participants who are not rechallenged with study intervention, the

participant should be discontinued from the study and complete an ET visit (Visit 7/ET) and 4-week follow-up visit. Participants should receive appropriate follow-up as per standard of care.

The investigator must contact the sponsor medical monitor to discuss all cases of confirmed ALT/AST elevation $\geq 3 \times \text{ULN}$. All ALT/AST elevations must be followed until ALT and AST return to $< 1.5 \times \text{ULN}$ and there is full clinical resolution.

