9.5.1 Potential Hy's Law Cases

Sites must report every participant who meets the following potential Hy's law criteria if this occurs within the time the participant signs the ICF until 30 days after the last dose of investigational product:

- ALT or AST $\geq 3 \times \text{ULN}$ AND
- Total bilirubin $\geq 2 \times \text{ULN}$ AND
- Alkaline phosphatase $< 2 \times \text{ULN}$

Study site personnel must report every participant who meets these criteria. Typically, all 3 analytes will be obtained from the same sample, but they may come from multiple samples taken within a 24-hour period. This requirement applies from the time the participant signs the ICF for the study until 30 days after the final protocol-defined study visit or the last known dose of study intervention (if the final visit does not occur).

A laboratory alert for possible Hy's law cases will be in place and must notify investigators and the sponsor immediately when the above criteria have been met. A possible Hy's law case must be faxed to the sponsor on an abnormal liver function reporting form as soon as possible (within 24 hours of learning of the possible Hy's law case) to the fax number on the form or the SAE fax number, even if no AE has occurred. If the event is serious, please complete the SAE form. The eCRF for possible Hy's law cases must be completed within 7 calendar days. Every effort to determine the cause of the liver enzyme abnormalities must be made, and close monitoring should be initiated in conjunction with the medical monitor and medical safety physician and in accordance with the FDA Guidance for Industry, Drug-Induced Liver Injury: Premarketing Clinical Evaluation, July 2009. The participant should return to the study site and be evaluated as soon as possible, preferably within 48 hours from the time the investigator becomes aware of the abnormal results. This evaluation should include laboratory tests, detailed history, and physical assessment.

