The number and percentage of participants meeting each of the following criteria for postbaseline hepatic laboratory abnormalities listed in [Table 11.2-2](#) will be summarized by treatment group. The percentages will be calculated relative to the number of participants with at least 1 available postbaseline assessment. The numerator will be the total number of participants having at least 1 postbaseline value that meets the specific category during the study. A supportive listing will also be provided.

Table 11.2-2. Criteria for Hepatic Laboratory Abnormalities

Laboratory Parameter	Categories
ALT	$\geq 1 \times \text{ULN}$
	$\geq 1.5 \times \text{ULN}$
	$\geq 2 \times \text{ULN}$
	$\geq 3 \times \text{ULN}$
	$\geq 5 \times \text{ULN}$
	$\geq 10 \times \text{ULN}$
	$\geq 20 \times \text{ULN}$
AST	$\geq 1 \times \text{ULN}$
	$\geq 1.5 \times \text{ULN}$
	$\geq 2 \times \text{ULN}$
	$\geq 3 \times \text{ULN}$
	$\geq 5 \times \text{ULN}$
	$\geq 10 \times \text{ULN}$
	$\geq 20 \times \text{ULN}$
ALT or AST	$\geq 1 \times \text{ULN}$
	$\geq 1.5 \times \text{ULN}$
	$\geq 2 \times \text{ULN}$
	$\geq 3 \times \text{ULN}$
	$\geq 5 \times \text{ULN}$
	$\geq 10 \times \text{ULN}$
	$\geq 20 \times \text{ULN}$
Bilirubin Total	$\geq 1 \times \text{ULN}$
	$\geq 1.5 \times \text{ULN}$
	$\geq 2 \times \text{ULN}$
	$\geq 3 \times \text{ULN}$
	$\geq 5 \times \text{ULN}$
	$\geq 10 \times \text{ULN}$
	$\geq 20 \times \text{ULN}$
Alkaline Phosphatase	$\geq 1 \times \text{ULN}$
	$\geq 1.5 \times \text{ULN}$
	$\geq 2 \times \text{ULN}$
	$\geq 3 \times \text{ULN}$
	$\geq 5 \times \text{ULN}$
	$\geq 10 \times \text{ULN}$
	$\geq 20 \times \text{ULN}$
Concurrent Elevations ¹	ALT or AST $\geq 3 \times \text{ULN}$ and Bilirubin Total $\geq 1.5 \times \text{ULN}$
	ALT or AST $\geq 3 \times \text{ULN}$ and Bilirubin Total $\geq 2 \times \text{ULN}$
Potential Hy's Law ¹	ALT or AST $\geq 3 \times \text{ULN}$ and Bilirubin Total $\geq 2 \times \text{ULN}$ and ALP $< 2 \times \text{ULN}$

ALT = alanine aminotransferase; AST = aspartate aminotransferase; TBL = total bilirubin; ALP = alkaline phosphatase; ULN = upper limit of normal (value provided by the laboratory).

¹ Elevations are from the same day

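### The bilirubin stopping criterion in Protocol 9.5 is strictly above 2 x ULN, so a potential Hy's law case at exactly 2.0 x ULN falls outside it

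*Protocol*

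**What the plan says.** Protocol 9.5 introduces its stop list with "Study intervention must be discontinued if any of the following criteria are met", so the list is mandatory and one criterion is enough. The bilirubin criterion is "ALT or AST $\geq 3 \times$ ULN and total bilirubin $> 2 \times$ ULN". The other four cover:

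- transaminases at or above 3 x ULN with listed symptoms or eosinophilia above 5%;
- transaminases at or above 3 x ULN with INR above 1.5;
- transaminases at or above 5 x ULN lasting more than two weeks;
- transaminases at or above 8 x ULN.

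Protocol 9.5.1 defines a potential Hy's law case by three conditions: "ALT or AST $\geq 3 \times \text{ULN}$ AND" "Total bilirubin $\geq 2 \times \text{ULN}$ AND" alkaline phosphatase below 2 x ULN. Protocol 6.5.2, which makes such a case an event of special interest, also uses "an elevated total bilirubin lab value that is $\geq 2 \times \text{ULN". SAP Table 11.2-2 agrees: "Bilirubin Total $\geq 2 \times \text{ULN}$ and ALP $< 2 \times \text{ULN".

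For these cases, 9.5.1 requires a report within 24 hours, prompt evaluation and close monitoring. It also sets up a laboratory alert that "must notify investigators and the sponsor immediately when the above criteria have been met". It gives no instruction to stop dosing. Under 9.5 the investigator "must contact the sponsor medical monitor to discuss all cases of confirmed ALT/AST elevation" at or above 3 x ULN. That obliges a discussion, not a stop.

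**The concern.** The documents state the same bilirubin threshold in two ways. Everywhere the liver signal is defined, reported or tabulated, the threshold is inclusive. In the one place where it forces the drug to be stopped, it is strict. At the boundary, a participant can trigger the Hy's law alert and the 24-hour report without meeting the bilirubin criterion that would require a stop.

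The withdrawal criteria in Protocol 8.9 do not close this gap, because on liver tests they refer only to the discontinuation criteria in 9.5. The rechallenge control in 9.5 follows from the stop list, so a participant who was never required to stop is not formally subject to it.

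What is at stake is participant safety in a rare case, not the trial's inference. The protocol treats liver safety as a central concern: Section 1.2 records that ALT increases ended development of earlier oral drugs in this class, and Section 3.3 sets up an adjudication committee for transaminase elevations.

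**Working it through.** The plan states no figure on this point to reproduce. The check compares the two rules at and around the boundary and then asks whether the boundary value can occur.

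**Step 1. The rules as logical conditions.** Let T be the larger of ALT and AST, B total bilirubin and P alkaline phosphatase, each as a multiple of its ULN.

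- Potential Hy's law (Protocol 6.5.2 and 9.5.1; SAP Table 11.2-2): T ≥ 3 and B ≥ 2 and P < 2.
- Bilirubin stop criterion (Protocol 9.5): T ≥ 3 and B > 2.

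**Step 2. Compare them with T ≥ 3 and P < 2.**

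| Bilirubin | Potential Hy's law? | Bilirubin stop criterion met? |
|---|---|---|
| Below 2.0 x ULN | No | No |
| Exactly 2.0 x ULN | Yes | No |
| Above 2.0 x ULN | Yes | Yes |

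The rules disagree at one value only.

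**Step 3. Do the other four criteria force a stop at that value?** Not necessarily. Take T = 4, B = 2.0, P = 1, INR at or below 1.5, no listed symptoms and eosinophils at or below 5%. The symptom and INR criteria are not met, and T is below both 5 and 8. None of the five criteria applies, yet the participant is a potential Hy's law case.

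**Step 4. Can the value be reported?** SAP Table 20.1-1 gives total bilirubin to one decimal in mg/dL. The documents do not state this trial's ULN. The layout example in SAP Table 20.2-1 shows 18.81 µmol/L (1.1 mg/dL), which is used here only as an illustration.

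- Conversion factor: 18.81 / 1.1 = 17.1 µmol/L per mg/dL.
- Boundary: 2 x 1.1 = 2.2 mg/dL = 2.2 x 17.1 = 37.62 µmol/L. This meets the inclusive rule but not the strict one.
- Next one-decimal value: 2.3 mg/dL = 2.3 x 17.1 = 39.33 µmol/L, and 2.3 / 1.1 = 2.09 x ULN. This meets both rules.

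Only 2.2 mg/dL falls between the two rules. For assumed ULNs of 1.0, 1.2 or 1.3 mg/dL, the value in the gap is 2.0, 2.4 or 2.6 mg/dL. If results and the ULN are reported to the same precision, 2 x ULN is always a reportable result, so the point does not depend on the 1.1 example.

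**Step 5. After the change.** With B ≥ 2 in the stop criterion, any case with T ≥ 3, B ≥ 2 and P < 2 also satisfies T ≥ 3 and B ≥ 2. Every potential Hy's law case in a participant on study drug would then meet the stop rule.

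**The case against.** The strongest reply is that the two rules do different jobs and nothing says they must match. Section 9.5.1 is a reporting net that starts at consent, before any dose, and carries an alkaline phosphatase condition. Section 9.5 governs participants on drug and has no such condition. The protocol already reports more than it stops: a transaminase of 3 x ULN alone is reportable but does not force discontinuation. On this view, the strict sign may be a deliberate choice.

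Several safeguards also narrow the exposure:

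- Protocol 8.9 lets the investigator withdraw from treatment a participant judged to be at significant risk.
- Protocol 9.5 calls for repeat testing within 48 to 72 hours and, once the elevation is confirmed, generally one or two chemistry panels a week. Any retest with transaminases still at or above 3 x ULN and bilirubin above 2.0 x ULN triggers the mandatory stop.
- Section 9.5.1 refers to an FDA guidance on liver injury. It is not among the documents, so what it would add cannot be judged here.

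The remedy may also come late. SAP 10.3.2.1 refers to participant numbers already observed, and the SAP change log runs to January 2022.

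These points are fair, and they limit the weight of the finding. None makes stopping mandatory at 2.0 x ULN, since the authority in 8.9 is discretionary. None gives a reason for leaving a potential Hy's law case outside the bilirubin stop criterion when a case marginally above it is inside.

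**Conclusion.** The mismatch is real and is confined to one value. At exactly 2.0 x ULN, with ALT or AST at least 3 x ULN and alkaline phosphatase below 2 x ULN, a participant is a potential Hy's law case who does not meet the bilirubin stop criterion. Stopping then depends on another criterion being met or on clinical judgment. This does not mean such a participant would stay on drug; the broad symptom criterion in particular may well apply.

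The practical size is very small. The documents give no event rate, and very few or no participants are likely to be affected. The mg/dL values above rest on assumed ULNs and one-decimal reporting. The logical gap rests on neither. This is a minor, optional improvement, worth making because it concerns a liver-safety stopping rule and moves that rule in the safer direction.

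**What to change.** In the second criterion of the stop list in Protocol 9.5, change the bilirubin condition from > 2 x ULN to ≥ 2 x ULN. Leave the Hy's law definition in Protocol 6.5.2 and 9.5.1 and in SAP Table 11.2-2 unchanged. The laboratory alert also needs no change, because it already fires on the 9.5.1 criteria.

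The cost is one symbol, carried in the next amendment with the usual IRB/IEC review, and at most a rare additional stop. Such a stop can be reversed, since 9.5 allows rechallenge after consultation with the medical monitor. If dosing in this trial has ended, check the extension-study protocols for the same wording and correct it there; their text is not among these documents.

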9.5.1 Potential Hy's Law Cases

Sites must report every participant who meets the following potential Hy's law criteria if this occurs within the time the participant signs the ICF until 30 days after the last dose of investigational product:

- ALT or AST $\geq 3 \times \text{ULN}$ AND
- Total bilirubin $\geq 2 \times \text{ULN}$ AND
- Alkaline phosphatase $< 2 \times \text{ULN}$

Study site personnel must report every participant who meets these criteria. Typically, all 3 analytes will be obtained from the same sample, but they may come from multiple samples taken within a 24-hour period. This requirement applies from the time the participant signs the ICF for the study until 30 days after the final protocol-defined study visit or the last known dose of study intervention (if the final visit does not occur).

A laboratory alert for possible Hy's law cases will be in place and must notify investigators and the sponsor immediately when the above criteria have been met. A possible Hy's law case must be faxed to the sponsor on an abnormal liver function reporting form as soon as possible (within 24 hours of learning of the possible Hy's law case) to the fax number on the form or the SAE fax number, even if no AE has occurred. If the event is serious, please complete the SAE form. The eCRF for possible Hy's law cases must be completed within 7 calendar days. Every effort to determine the cause of the liver enzyme abnormalities must be made, and close monitoring should be initiated in conjunction with the medical monitor and medical safety physician and in accordance with the FDA Guidance for Industry, Drug-Induced Liver Injury: Premarketing Clinical Evaluation, July 2009. The participant should return to the study site and be evaluated as soon as possible, preferably within 48 hours from the time the investigator becomes aware of the abnormal results. This evaluation should include laboratory tests, detailed history, and physical assessment.

9.6 Procedures for Unmasking of Study Medication

The IWRS will be programmed with blind-breaking instructions. In case of an emergency, the investigator has the sole responsibility for determining if unblinding of a participant's study intervention assignment is warranted. Participant safety must always be the first consideration in making such a determination. If the investigator decides that unblinding is warranted, the investigator should make every effort to contact the sponsor medical monitor prior to unblinding a participant's study intervention assignment unless this could delay emergency treatment of the participant. If a participant's study intervention assignment is unblinded, the sponsor medical monitor must be notified within 24 hours after breaking the blind. The date and reason that the blind was broken must be recorded in the source documentation.

10. Administrative Items

This protocol is to be conducted in accordance with the applicable GCP regulations and guidelines (eg, the ICH Guideline on GCP) and applicable regulations in relevant countries.

10.1 Protection of Human Participants

10.1.1 Compliance With Informed Consent Regulations (US 21 CFR Part 50) and Relevant Country Regulations

Written informed consent is to be obtained from each participant prior to any study-related activities or procedures in the study, and/or from the participant's legally authorized representative.

The following process will be followed:

- The investigator or his/her representative will explain the nature of the study to the participant or his/her legally authorized representative and answer all questions regarding the study.
- Participants must be informed that their participation is voluntary. Participants or their legally authorized representatives will be required to sign a statement of informed consent that meets the requirements of 21 CFR 50, local regulations, ICH guidelines, HIPAA requirements, where applicable, and the IRB/IEC or study center.
- The medical record must include a statement that written informed consent was obtained before the participant was enrolled in the study and the date the written consent was obtained. The authorized person obtaining the informed consent must also sign the ICF.

- Participants must be re-consented to the most current version of the ICF(s) during their participation in the study if required by the IRB.
- A copy of the ICF(s) must be provided to the participant or the participant's legally authorized representative.

10.1.2 Compliance With IRB or IEC Regulations

This study is to be conducted in accordance with IRB regulations (US 21 CFR Part 56.103) or applicable IEC regulations. The investigator must obtain approval from a properly constituted IRB/IEC prior to initiating the study and re-approval or review at least annually. The sponsor is to be notified immediately if the responsible IRB/IEC has been disqualified or if proceedings leading to disqualification have begun. Copies of all IRB/IEC correspondence with the investigator should be provided to the sponsor.

10.1.3 Compliance With Good Clinical Practice

This protocol is to be conducted in accordance with the applicable GCP regulations and guidelines.

10.1.4 Compliance With Electronic Records; Electronic Signatures Regulations (US 21CFR Part 11)

This study is to be conducted in compliance with the regulations on electronic records and electronic signature.

10.2 Financial Disclosure

Investigators and subinvestigators will provide the sponsor with sufficient, accurate financial information as requested to allow the sponsor to submit complete and accurate financial certification or disclosure statements to the appropriate regulatory authorities. Investigators are responsible for providing information on financial interests during the course of the study and for 1 year after completion of the study.

10.3 Changes to the Protocol

The investigator must not implement any deviation from or changes of the protocol without approval by the sponsor and prior review and documented approval/favorable opinion from the IRB/IEC (and the appropriate regulatory agency, if required by national law) of a protocol amendment, except where necessary to eliminate immediate hazards to study participants, or

when the changes involve only logistical or administrative aspects of the study (eg, change in monitors, change of telephone numbers).

10.4 Data Protection

Participants will be assigned a unique identifier. Any participant records or datasets that are transferred to the sponsor will contain the identifier only; participant names or any information which would make the participant identifiable will not be transferred.

The participant must be informed that his/her personal study-related data will be used by the sponsor in accordance with local data protection law. The level of disclosure must also be explained to the participant.

The participant must be informed that his/her medical records may be examined by Clinical Quality Assurance auditors or other authorized personnel appointed by the sponsor, by appropriate IRB/IEC members, and by inspectors from regulatory authorities.

10.5 Participant Confidentiality

A report of the results of this study may be published or sent to the appropriate health authorities in any country in which the study intervention may ultimately be marketed, but the participant's name will not be disclosed in these documents. The participant's name may be disclosed to the sponsor of the study, or the governing health authorities or the FDA if they inspect the study records. Appropriate precautions will be taken to maintain confidentiality of medical records and personal information.

10.6 Participant Privacy

Written authorization (United States sites only), data protection consent (European sites only), and other documentation in accordance with the relevant country and local privacy requirements (where applicable) is to be obtained from each participant prior to enrollment into the study, and/or from the participant's legally authorized representative in accordance with the applicable privacy requirements (eg, HIPAA, European Union Data Protection Directive 95/46/EC ["EU Directive"]).

In accordance with HIPAA requirements, additional purposes of this study may include publishing of anonymous participant data from the study.

